Conventional treatment includes wait and see approach for asymptomatic patients, erythropoiesis-stimulating agents, androgens or immunomodulatory agents for anemia, cytoreductive drugs such as hydroxyurea for splenomegaly and constitutional symptoms, and splenectomy or radiotherapy for selected patients.²⁰ Currently, ruxolitinib, a dual JAK-1 and -2 inhibitor, is the only targeted therapy approved for the treatment of myelofibrosis in the United States and European Union. While the approval of ruxolitinib has changed the treatment landscape for patients with myelofibrosis, it is still aimed at improving symptoms and quality of life. The only treatment modality capable of curing MF is allogenic HSCT. The applicability of HSCT is limited by the inherent risks in this population, with their attendant comorbidities.

Fedratinib, a JAK-2 specific inhibitor, is currently in clinical development and has been evaluated in patients with MF. The reported SVR₃₅ with fedratinib in the previously untreated population is similar that reported of ruxolitinib at approximately 40%. ^{21,22} A recent re-analysis of the JAKARTA-2 study of fedratinib in patients with MF that previously failed ruxolitinib treatment reports a SVR₃₅ of 30%. The most common adverse events in the JAKARTA-2 study in the ruxolitinib failure cohort are reported as anemia (100%), platelet count decrease (73%), creatinine increased (72%), diarrhea (65%), nausea (53%), and ALT increased (52%). Additionally, among the 600 subjects treated with fedratinib in clinical trials, 8 subjects were reported to have potential Wernicke's encephalopathy.²³

Navitoclax has been evaluated in 25 clinical studies as both single-agent and as combination therapy. Clinical studies have assessed the safety, pharmacokinetics and initial efficacy in subjects with hematologic malignancies or in subject with solid tumors. There is preclinical data that suggest that the combination of navitoclax with ruxolitinib may provide disease-modifying therapy for patients with PMF or SMF.

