A sample list of excluded medications and cautionary medications can be found in (Appendix H). Since a complete list of medications that are excluded or should only be used with caution cannot be provided, please refer to the appropriate product label and/or contact the AbbVie TA MD/SD whether a specific concomitant medication falls into the above mentioned categories. Information regarding potential drug interactions with navitoclax can also be located in the current navitoclax Investigator's Brochure.

If the investigator determines that use of an excluded or cautionary concomitant medication is medically indicated, the investigator will notify the AbbVie TA MD/SD and discuss the rationale for the use of the concomitant medication and the need to medically monitor the potential study subject under consideration.

Subjects Receiving Ruxolitinib

Ruxolitinib is predominantly metabolized by CYP3A4 and to a lesser extent by CYP2C9. For subjects who are taking strong CYP3A4 inhibitors (such as ketoconazole and clarithromycin) or moderate CYP3A4 inhibitors (such as fluconazole) concurrently with ruxolitinib study treatment, the local, approved product label should be referenced for ruxolitinib dose reduction, interruption, and discontinuation, or monitoring guidelines. The local, approved ruxolitinib product label should also be referenced for monitoring guidelines when co-administered with CYP3A inducers or drugs transported by P-gp and BCRP.

5.2.5 **Contraception Recommendations**

While participating in this research study, subjects should not become pregnant, breastfeed a baby or father a baby.

Contraception Requirements for Females

Subjects must follow the following contraceptive guidelines as specified:

Females, Non-Childbearing Potential

Females do not need to use birth control during or following study drug treatment if considered of non-childbearing potential due to meeting any of the following criteria:

- 1. Premenopausal female with permanent sterility or permanent infertility due to one of the following:
 - Permanent sterility due to a hysterectomy, bilateral salpingectomy, bilateral oophorectomy
 - Non-surgical permanent infertility due to Mullerian agenesis, androgen insensitivity, or gonadal dysgenesis; investigator discretion should be applied to determining study entry for these individuals.

2. Postmenopausal female

- Age > 55 years with no menses for 12 or more months without an alternative medical cause.

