- gg. Survival information (e.g., date and cause of death, post-treatment cancer therapies including systemic therapy, radiation therapy, cancer related-procedures and stem-cell transplant, response to post-treatment cancer therapies) will be collected via telephone calls (e.g., to subject or family member), clinic visits, and/or public database searched every 6 months (± 2 weeks) after the last study visit up to 5 years after TCV (provided informed consent has not been withdrawn for collection of such information).
- hh. Sample may be collected at Screening or Week 0 Day 1.

Table 7. Schedule of Pharmacokinetic Assessments for Navitoclax and Ruxolitinib

				Sampling Plan
Cohort	Visit Schedule	Before Drug Administration	After Drug Administration ^a	Specimen Matrix
1a	Day 1	Predose	2h, 4h, 6h, 8h	Blood → Plasma
	Day 2	Predose ^b		Frozen –20°C or colder
	Day 8 Day 15 Day 22 Day 29 Day 43 Week 8 (Day 57) Week 12 (Day 85) Week 24 (Day 169) Week 48 (Day 337)	Predose		
1b, 2°, 3	Day 1	Predose	Cohort 1b and 3: 4h Cohort 2: 2h, 4h, 6h, 8h	
	Day 2	Predose ^b		
	Day 15 Day 29 Week 8 (Day 57), Week 12 (Day 85), Week 24 (Day 169)	Predose		

h = hours; min = minute

On days when PK samples are collected pre-dose, navitoclax (all cohorts) and ruxolitinib (Cohort 1a, 1b, and 3) should be taken at the same time during the clinic visit following the blood sample collection.

The date and time of each PK sample collection and the date and time of the last two doses of navitoclax and/or ruxolitinib at each visit will be captured on the eCRF.

a. Samples for 2h and 4h should be collected within 10% of the scheduled time; Samples for 6h and 8h should be collected with ± 30 min.

obbie Navitoclax (ABT-263)

M16-109 Protocol Amendment 11 EudraCT 2017-001398-17

Table 7. Schedule of Pharmacokinetic Assessments for Navitoclax and Ruxolitinib (Continued)

- b. Collection is 24 hours (± 30 min) post-first dose of navitoclax on Day 1 and before dosing of navitoclax and morning dose of ruxolitinib (if applicable, e.g., Cohorts 1a, 1b and 3) on Day 2.
- Sampling schedule is for navitoclax only.

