# 8.0 Efficacy Analyses

#### 8.1 General Considerations

The primary analysis population for primary endpoint is the Full Analysis Set. Unless otherwise specified, the secondary efficacy endpoints and exploratory efficacy endpoints will be analyzed in Full Analysis Set.

All efficacy results will be presented by cohort unless stated otherwise. For all analyses, unless otherwise specified, data collected after the cutoff date will be excluded from statistical analysis. All spleen volume related endpoints described in Section 3.0 will be based on the assessments from the central review of the radiographic images by an Independent Review Committee (IRC) as described in the protocol.

abbyie Navitoclax/ABT-263

Navitoclax/ABT-263 M16-109 – Statistical Analysis Plan Version 4.0 – 31 January 2023

All response rates and the corresponding 95% confidence interval (Cl) using the Clopper-Pearson method will be provided.

For the analyses of all time-to-event endpoints, survivorship functions will be estimated using Kaplan-Meier product-limit methodology. If reached, median time-to-event and its 95% CI will be presented.

For the analyses of all continuous endpoints, such as change from baseline in score, the scores will be summarized with baseline mean, visit mean, mean change from baseline, mean percentage change from baseline, standard deviation, and the corresponding 95% CIs.

Baseline measurement related to each efficacy endpoint for analysis has been described in Section 7.0.

[figure not shown]
The post-study treatment refers to Post Study Drug Systemic Therapies for Myelofibrosis, Post Study Drug Radiation Therapy and Post Study Drug Transplant. The disease progression (DP) refers to relapse or progressive disease in the Disease Response Assessment Form.

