#### 8.3 Primary Efficacy Endpoint(s) and Analyses

## 8.3.1 Primary Efficacy Endpoint

#### Spleen Volume Reduction ≥ 35% at Week 24 (SVR35W24) per IWG Criteria

SVR35W24 rate is defined as the proportion of subjects who achieved at least 35% reduction from baseline spleen volume at Week 24. The analysis window for Week 24 is defined as Day 127 to Day 211 per study activity schedule. Data after the start of post-study treatment or disease progression (relapse and progressive disease) will be excluded from the analyses. Subjects who do not have percent change from baseline (missing baseline or missing post-baseline) of spleen volume in the analysis window will be considered as non-responders.

Primary analysis population for SVR35W24 is the Full Analysis Set (see Section 4.0 for the definition of Full Analysis Set).

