# 8.5.1.10 Overall Survival (OS)

OS is defined as time from the first date of study treatment to the date of death due to any cause. If a subject has not died, then the data will be censored on the date when the subject was last known alive.

The last known alive date will be determined by selecting the last available date of the following study procedures: last dose date of study treatment, start date of adverse event, bone marrow collection, disease assessment, spleen assessment, vital signs assessment, electrocardiogram assessment, clinical laboratory collection (including COVID-19 test), study drug administration, start date of concomitant or post-treatment medicine or procedure, last known alive date in survival follow-up, biospecimen sample collection, quality of life assessments, and performance status.

OS will be analyzed in the Full Analysis Set.

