## **Appendix A.** Protocol Deviations

The number and percentage of subjects who reported at least one of the following protocol deviation categories will be provided.

- Subject entered into the study even though s/he did not satisfy entry criteria.
- Subject developed withdrawal criteria during the study and was not withdrawn.
- Subject received wrong treatment or incorrect dose of study treatment.
- Subject took prohibited concomitant medication.

[figure not shown]

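### SAP 8.1 ties the efficacy cut-off to three post-study-drug categories, so splenectomy, and other MF therapy started before the last navitoclax dose, stop no efficacy data

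*SAP*

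**What the plan says.** SAP 8.1 defines *post-study treatment* in one sentence: "The post-study treatment refers to Post Study Drug Systemic Therapies for Myelofibrosis, Post Study Drug Radiation Therapy and Post Study Drug Transplant". For the primary endpoint, SAP 8.3.1 states: "Data after the start of post-study treatment or disease progression (relapse and progressive disease) will be excluded from the analyses". It adds: "The analysis window for Week 24 is defined as Day 127 to Day 211 per study activity schedule". A subject with no percent change in spleen volume in that window is a non-responder.

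The same term is a cut-off or censoring point for TSS50W24 (8.4.1.1), anemia response (8.4.1.2), fibrosis grade (8.4.1.3), the other SVR rates (8.5.1.1), duration of SVR35 (8.5.1.2), palpable spleen length (8.5.1.3), TSS50 (8.5.1.4), ORR (8.5.1.8), PFS (8.5.1.9) and the PRO changes.

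Three SAP sections show what *post* means. Section 7.1 makes the last navitoclax dose the last date of study treatment. Section 6.4 treats Cohort 1 ruxolitinib after that dose as post-study treatment. Section 7.5 keeps a separate concomitant category for medication taken during treatment.

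On the protocol side:
- Section 3.6 lists, among conventional MF treatments, "cytoreductive drugs such as hydroxyurea for splenomegaly and constitutional symptoms, and splenectomy or radiotherapy for selected patients".
- Section 5.2.2 bars prior splenectomy at entry. No rule for splenectomy during the study was found.
- Section 5.2.4 prohibits anti-cancer, cytoreductive, radiation and named supportive MF therapy during treatment.
- Section 5.4.1 withdraws a subject from study treatment when alternative MF therapy is required.
- Appendix C, Table 6, note gg collects in survival follow-up "post-treatment cancer therapies including systemic therapy, radiation therapy, cancer related-procedures and stem-cell transplant".

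SAP Appendix A tabulates deviations, including "Subject took prohibited concomitant medication" and subjects who met withdrawal criteria but were not withdrawn. No efficacy rule is attached.

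**The concern.** The SAP's strategy is to remove efficacy data obtained after other MF therapy. The definition that carries the strategy leaves out two things: splenectomy or another splenic procedure, on or off navitoclax, and MF therapy begun while navitoclax continues. The second is concomitant in the SAP's own terms, so the post-study cut-off is not reached.

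If either occurs, its effect on spleen size, symptoms or time to progression stays in the analysis of navitoclax. The study is open-label and non-randomized, so no comparator would reveal it. An analyst following so explicit a definition would have no reason to fill the gap.

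**Working it through.** **Which events stop the data**

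| Event | In the SAP 8.1 list? | Other safeguard | What remains |
|---|---|---|---|
| Systemic MF therapy, radiation or transplant after the last navitoclax dose | Yes | none needed | Nothing |
| Systemic MF therapy or splenic radiation started before the last dose | Not as worded | Prohibited (5.2.4); withdrawal (5.4.1) | Deviations and short overlaps |
| Splenectomy on navitoclax | No | Withdrawal (5.4.1), if seen as alternative MF therapy | No cut-off at the date of surgery |
| Splenectomy after navitoclax | No | Few efficacy assessments scheduled | Mainly PFS and SVR35 duration |

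Disease progression recorded earlier still cuts off the data in every row.

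**Endpoint by endpoint**

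- *Palpable length.* Response is a reduction of at least 50% at any time. Palpation is required at visits, and nothing says how a removed spleen is entered.
- *TSS50W24 and TSS50.* The diary runs daily to Week 36. Scores after an uncaught therapy or splenectomy remain in.
- *Duration of SVR35.* The spleen event needs an increase of at least 25% from nadir, which cannot occur without a spleen. Investigator-assessed relapse or progression still ends the duration.
- *PFS.* SAP Table B-4 has six progressive-disease criteria, and four are spleen-based. After splenectomy those four cannot occur. The two blast-based criteria, relapse and death still can. A death after splenectomy would count as an event, whereas SAP 8.5.1.9 ignores a death after listed post-study therapy. The direction of the effect on PFS is therefore not fixed.
- *Anemia.* Erythropoietin and its mimetics are handled in the response definition (8.4.1.2) and in its duration (8.5.1.7, Tables 6 and 7), but only for baseline transfusion-independent subjects. Danazol and steroids are not covered, and the transfusion-dependent definition has no such rule.
- *SVR35W24.* Hydroxyurea or splenic radiation overlapping navitoclax could contribute to a scan read as response. The window extends 211 − 169 = 42 days past the nominal visit. For splenectomy the SAP does not choose between zero volume (responder) and no measurement (non-responder under 8.3.1).

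**Size**

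The estimator was checked first. Exact Clopper-Pearson limits reproduce all 12 rows of SAP Table 1 to two decimals, for example 16/34 = 47.06% (29.78 to 64.87) and 12/30 = 40.00% (22.66 to 59.40).

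The shift per affected responder is 1/n: 1/34 = 2.9 points, 1/80 = 1.25, 1/70 = 1.4 and 1/30 = 3.3. Both 70 and 80 are shown for Cohort 1b because Table 1 uses 70, while the Full Analysis Set is all treated subjects, planned at about 80.

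The documents give no count of affected subjects. Taking 0 to 3 responders as an assumption and reclassifying them as non-responders:

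| Starting rate | 0 | 1 | 2 | 3 |
|---|---|---|---|---|
| 9/34 (preliminary Cohort 1a, protocol 3.4) | 26.47% (12.88–44.36) | 23.53% (10.75–41.17) | 20.59% (8.70–37.90) | 17.65% (6.76–34.53) |
| 32/70 (SAP Table 1) | 45.71% (33.74–58.06) | 44.29% (32.41–56.66) | 42.86% (31.09–55.25) | 41.43% (29.77–53.83) |
| 12/30 (SAP Table 1) | 40.00% (22.66–59.40) | 36.67% (19.93–56.14) | 33.33% (17.29–52.81) | 30.00% (14.73–49.40) |

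**The case against.** The strongest reply is that the protocol already closes most of the route. Section 5.2.4 prohibits the drugs and radiotherapy in question, 5.4.1 removes a subject who needs alternative MF therapy, and Appendix A of the SAP reports breaches. After navitoclax stops, no diary is scheduled, and imaging and marrow are done only if progression is suspected. Anemia data end 30 days after the last dose. This stands, and it limits the exposure to deviations, short overlaps and splenectomy. It does not tell the analyst what to do with the data when one of these occurs.

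It is also fair that the case report forms and the Statistical Programming Plan are not available. A post-study-drug form might in practice hold therapy begun during navitoclax. If so, the SAP should say so.

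Several stronger readings are tempting, and the documents do not support them:
- *Splenectomy counts as an SVR35W24 response.* The SAP does not say, and its missing-data rule may make such a subject a non-responder.
- *The protocol foresees MF drugs being used when needed.* The sentence beginning "If the investigator determines that use of an excluded or cautionary concomitant medication is medically indicated" closes the drug-interaction text for navitoclax and refers to Appendix H, which lists anticoagulants, antiplatelet drugs, NSAIDs, antidepressants and metabolic or transporter agents. The MF-therapy bans are separate.
- *Note gg proves an omission.* It belongs to survival follow-up, which subjects enter after progression or new MF therapy. It shows what is collected, not what the cut-off was meant to contain.
- *Progression cannot be recorded after splenectomy.* Relapse, the blast-based criteria and death remain.
- *Cohort 2 is the cohort most affected.* The documents give no data on this.

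**Conclusion.** The point holds in limited form. The SAP 8.1 definition, read with 6.4, 7.1 and 7.5, leaves splenectomy at any time and MF therapy begun before the last navitoclax dose without an efficacy rule. Palpable length, TSS50, SVR35 duration and PFS are the clearest cases. SVR35W24 is exposed to overlapping drug or radiation therapy and is undefined for splenectomy.

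The size is 2.9, 1.25 to 1.4, or 3.3 points per affected responder, depending on the cohort. The total rests on an assumed count that may be zero. Response rates could only be too high from therapies that add responders. A removed spleen could be scored either way on the primary endpoint, and the effect on PFS can go either way. Sample sizes and the planned intervals are not affected. It is a cheap improvement that makes the SAP's own strategy complete, not evidence that a result is wrong.

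**What to change.** In SAP 8.1, define the cut-off as the earliest start, on or after Day 1 and regardless of whether navitoclax has stopped, of any of the following:
- non-study MF-directed systemic therapy;
- splenic radiation;
- splenectomy or another splenic procedure;
- transplant.

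Take the date from the concomitant medication, procedure and post-study forms. Use it wherever the SAP now refers to the start of post-study treatment. Add one sentence stating that spleen volume or length measured after splenectomy is not counted as a response.

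The cost is one definition, one derived date per subject and a short medical review of concomitant therapies. The inputs appear to exist already: protocol 5.3.1.1 records all medications until 30 days after the last dose, and SAP 8.5.1.10 already uses the "start date of concomitant or post-treatment medicine or procedure". Some response rates may come out slightly lower.

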# 8.2 Handling of Missing Data

Missing data for all time-to-event endpoints will be handled by appropriate censoring in analysis and the censoring rule will be described in the following sub-sections.

Unless otherwise specified, for the analyses of all response rates, subjects without response will be considered as non-responders.

No missing data imputation will be applied for change from baseline in PRO domain score.

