5.4 Removal of Subjects from Therapy or Assessment

5.4.1 **Discontinuation of Individual Subjects**

Each subject has the right to withdraw from the study (study treatment and/or follow-up) at any time. In addition, the Investigator may discontinue a subject from treatment at any time for any reason if the Investigator considers it necessary, including the occurrence of an adverse event or noncompliance with the protocol.

During the COVID 19 pandemic, it has been necessary to employ mitigation strategies to enable the investigator to ensure subject safety and continuity of care. Acceptable mitigation strategies are identified and included within this protocol.

Each subject will be withdrawn from study treatment (as applicable) if any of the following occur:

- The subject has disease progression as defined in Appendix E, and the Investigator feels the subject is no longer benefiting from treatment.
- The subject requires alternative therapy for treatment of MF.
- The subject experiences treatment toxicity which, in the Investigator's opinion, prohibits further therapy or the Investigator believes it is otherwise in the best interest of the subject.
- Significant subject noncompliance with study drug administration, study procedures or study requirements.
- Subject becomes pregnant or begins breastfeeding.
- The subject decides to withdraw consent of being treated by study treatment for any reason.
- Any other medical reason that AbbVie or the study Investigator deems appropriate.

Discussion with the TA MD/SD is recommended before discontinuing a subject from the study for any reason other than described above to ensure all acceptable mitigation steps have been evaluated.

In the event that a subject discontinues study treatment, the reason(s) for the discontinuation and the primary reason will be recorded and a TCV will be performed as soon as possible after discontinuation from study treatment.

If a subject is discontinued from study treatment or the study with an ongoing adverse event, the Investigator will attempt to provide follow-up until a satisfactory clinical resolution of the adverse event is achieved.

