# 2.1 Objectives and Hypotheses

The primary objective of the study is to:

• Evaluate the effect of navitoclax alone or in combination with ruxolitinib on spleen volume.

The secondary objectives of the study are:

- To assess the effect of navitoclax alone or in combination with ruxolitinib on total symptom score (TSS) as assessed by the Myelofibrosis Symptom Assessment Form (MFSAF) version 4.0 diary.
- To evaluate the effect of navitoclax alone or in combination with ruxolitinib on bone marrow fibrosis.

- To determine the rate of anemia response associated with navitoclax alone or in combination with ruxolitinib.
- To describe the safety profile and PK profile observed with navitoclax alone or in combination with ruxolitinib.

The exploratory objectives of the study are:

- To evaluate the effect of navitoclax alone or in combination with ruxolitinib on the onset, magnitude, and duration of disease response, including effects on spleen and anemia.
- To evaluate the effect of navitoclax alone or in combination with ruxolitinib on measures of health-related quality of life including total symptom score, fatigue, and physical functioning.
- To evaluate the effect of navitoclax alone or in combination with ruxolitinib on overall survival and progression free survival.
- Exploration of biomarkers predictive of navitoclax activity and response may be performed.

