#### 8.5.1.5 Change in MFSAF Score

[figure not shown]
Change in average daily MFSAF score of weekly interval (7-day) for each item and TSS (except for Week 23 and Week 25) from baseline will be summarized according to the scoring approach provided in Appendix C. Data after the start of post-study treatment, disease progression will not be included in the analyses. Change in MFSAF score will be analyzed among subjects who had baseline and post-baseline MFSAF score.

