#### 8.5.1.11 Change in PROMIS Fatigue Score

Change in PROMIS fatigue score is defined as the change from baseline score by Visit. The scores are collected using PROMIS Fatigue SF7a. The summary score, symptom and impact scores will be calculated according to the scoring algorithm specified in Appendix C. Data after the start of post-study treatment, disease progression will not be included in the analyses. Change in PROMIS Fatigue Score will be analyzed among subjects who had baseline and post-baseline PROMIS Fatigue Score.

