#### 8.5.1.12 Change in EORTC QLQ-C30 Score

Change in EORTC QLQ-C30 score is defined as the change from baseline score by Visit. The scores are collected using EORTC QLQ-C30. The summary score of EORTC QLQ-C30 will be calculated according to the scoring algorithm specified in Appendix C. Data after the start of post-study treatment, disease progression will not be included in the analyses. Change in EORTC QLQ-C30 Score will be analyzed among subjects who had baseline and post-baseline EORTC QLQ-C30 score.

[figure not shown]

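### Visit means of change in MFSAF, PROMIS Fatigue and EORTC QLQ-C30 cover only subjects still observed and progression-free, so these exploratory results are likely to drift toward apparent benefit; add n per visit and a repeated-measures estimate.

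*SAP*

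**What the plan says.** SAP 2.1 has an exploratory objective on the effect of navitoclax on "measures of health-related quality of life including total symptom score, fatigue, and physical functioning". SAP 3.3 lists the matching endpoints, change in MFSAF, PROMIS and EORTC QLQ-C30 scores, as exploratory.

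The analysis comes from several places that must be read together:

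- **Missing scores, SAP 8.2:** "No missing data imputation will be applied for change from baseline in PRO domain score".
- **Summary method, SAP 8.1:** continuous endpoints are described by baseline mean, "visit mean, mean change from baseline, mean percentage change from baseline", SD and 95% CIs. SAP 8.5.2 only refers back to 8.1. No model is specified.
- **Subjects, SAP 8.5.1.5, 8.5.1.11 and 8.5.1.12:** "Change in MFSAF score will be analyzed among subjects who had baseline and post-baseline MFSAF score"; "Change in PROMIS Fatigue Score will be analyzed among subjects who had baseline and post-baseline PROMIS Fatigue Score"; "Change in EORTC QLQ-C30 Score will be analyzed among subjects who had baseline and post-baseline EORTC QLQ-C30 score".
- **Cut-off, the same three sections:** "Data after the start of post-study treatment, disease progression will not be included in the analyses".
- **Meaning of progression, SAP 8.1:** it covers relapse as well as progressive disease.

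Protocol 5.4.1 withdraws a subject for progression only when progression has occurred "and the Investigator feels the subject is no longer benefiting from treatment". Treatment, and with it questionnaire collection, can therefore continue after progression.

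**The concern.** With no imputation and no model, a mean at a given visit can include only subjects who have a usable score at that visit. Two groups drop out of it: those who stopped and gave no further questionnaires, and those whose later scores are removed because they progressed or relapsed.

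The second removal can depend on the outcome being measured. In SAP Appendix B, losing Clinical Improvement counts as relapse, and Clinical Improvement can rest on a symptom response alone, that is, a TSS fall of at least 50%. A subject whose symptoms return can therefore be classed as relapsed, after which the later TSS values leave the TSS mean. EORTC and PROMIS are also scheduled at the Treatment Completion Visit, but for a subject who stops because of progression that visit would normally come after progression, so its score would be excluded.

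If the absent subjects are doing worse, the remaining mean moves toward benefit even when nobody improves. The cohorts are single-arm, so no control group shares the drift and shows it. The objective concerns the treated cohort, while the summary describes the part of it that is still observed and progression-free.

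**Working it through.** **Figure in the plan.** The documents state no expected value, SD, dropout rate or precision for these change scores, so there is nothing to reproduce. The design figures in SAP 2.4 concern spleen response and serious adverse events and are not touched.

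**Direction of benefit.** TSS runs from 0 to 70, with higher scores worse (Protocol 5.3.1.1). A lower PROMIS Fatigue score means less fatigue. Apparent benefit is therefore a lower mean for TSS and PROMIS Fatigue. For EORTC QLQ-C30 it is a higher mean on the functional, global and summary scores and a lower mean on the symptom scales.

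**Bias formula.** Let f be the share absent at a visit, and D the amount by which their mean change is worse than that of subjects still included. The mean over everyone is (1 − f) × included mean + f × absent mean. The included mean is therefore too favourable by f × D.

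**Yardsticks.** The minimum important difference is 5 points for EORTC QLQ-C30 (Protocol 5.3.1.1) and 3 points for PROMIS Fatigue (Protocol 5.3.1.1; SAP Appendix C). None is given for TSS.

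**Numbers (f and D are assumptions).**

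| f | f × D, D = 0 | D = 5 | D = 10 | D giving 3 points (3/f) | D giving 5 points (5/f) |
|---|---|---|---|---|---|
| 10% | 0 | 0.5 | 1.0 | 30 | 50 |
| 20% | 0 | 1.0 | 2.0 | 15 | 25 |
| 30% | 0 | 1.5 | 3.0 | 10 | 16.7 |
| 40% | 0 | 2.0 | 4.0 | 7.5 | 12.5 |

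Against the EORTC yardstick, 1.0 point is 1.0/5 = 20% and 3.0 points is 3.0/5 = 60%. Against the PROMIS yardstick, 3.0 points is the whole minimum important difference.

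**How large a gap could selection produce?** An illustrative simulation set the true mean change at 0. Absence became more likely with worsening, with odds ratios of 1.5, 2 and 3 per SD. With SD 10 and 30% absent, the false improvement was 1.1, 1.9 and 2.7 points. Over SD 8 to 12 and 20% to 40% absent, it ran from 0.65 to 4.3 points. It was about 0 when absence was unrelated to change.

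**Would a model help?** Two illustrations used four visits, a true change of +5 and a between-visit correlation of 0.6.

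- *Dropout driven by the previous, recorded score (missing at random).* With SD 10 the raw mean was 6.0 at 20% missing and 6.6 at 33%. With SD 15 it was 7.4 at 24% and 8.7 at 37%. A normal-likelihood estimate gave 5.0 to 5.1 throughout, as it should when its assumption is built in.
- *Dropout driven by the current, unseen score (SD 15).* At about 25% missing the raw mean was 6.4 and the likelihood estimate 5.5 to 5.6. At 29% they were 8.0 to 8.1 and 6.3 to 6.4. The model reduced the bias and did not remove it.

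In the second illustration, the sampling SD of the mean at n = 30 was about 3 points.

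**The case against.** The case for leaving the plan alone is substantial.

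- **The endpoints are exploratory and descriptive.** Protocol 8.3 plans no formal test. The symptom endpoints TSS50W24 (secondary) and TSS50 (exploratory) count subjects with missing scores as non-responders (SAP 8.4.1.1, 8.5.1.4), so the reader already has TSS results in which dropout is failure. This stands, and it limits the importance of the point.
- **The cut-off is disclosed and consistent.** SAP 8.3.1, 8.4.1.1, 8.4.1.3, 8.5.1.3 and 8.5.1.4 apply it to spleen volume, TSS response, fibrosis, palpable spleen and TSS50. A summary while progression-free is a legitimate choice of estimand, and dropping the cut-off only for mean change would put TSS change and TSS response on different data. This stands too. SAP 8.6.1 does keep post-progression data for allele frequency, so a sensitivity analysis that retains them would not be foreign to the plan.
- **Absent subjects need not have worse symptoms.** Progressive disease is defined by spleen and blasts, and relapse also covers loss of anaemia or spleen response. The MFSAF diary ends at Week 36, which limits the effect on TSS. This weakens the presumption but does not remove it, because loss of a symptom response remains one route to relapse.
- **The lack of imputation is not itself a fault.** A mixed model imputes nothing explicitly, so the sentence in SAP 8.2 is compatible with the fix. The issue comes from combining it with raw means and the exclusion rules.

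A reader might infer that the reported benefit will be overstated as a matter of fact. The documents do not support that: they give neither the share absent nor the gap, and the bias is zero if the gap is zero.

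**Conclusion.** The point holds as a cheap improvement to exploratory analyses. The SAP reports observed, progression-free means without a model, and nothing in it offsets possible selection in the change-score means. Drift toward apparent benefit is the expected direction. It rests on the assumption that absent subjects are doing worse, which the relapse definition makes plausible, most directly for TSS.

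The size cannot be computed from the documents. The working examples run from 0 to 4.0 points by formula, with 1.0 point (20% absent, gap 5) and 3.0 points (30% absent, gap 10) as reference cases. Every one depends on assumed inputs.

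Three stronger readings should be avoided. First, the primary endpoint and TSS50W24 are not affected, since both count missing subjects as non-responders. Second, it would be wrong to say that all the means drift upward: for TSS and PROMIS Fatigue, benefit is a fall. Third, the progression cut-off need not be replaced. It is an estimand choice shared with other efficacy endpoints, so relaxing it belongs in a sensitivity analysis.

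**What to change.** For TSS, PROMIS Fatigue and EORTC QLQ-C30, amend SAP 8.5.1.5, 8.5.1.11, 8.5.1.12 and 8.5.2 as follows:

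1. Keep the raw visit means, show the number of subjects contributing at each visit, and label them as means among subjects observed and progression-free.
2. Add LS mean change with 95% CI by visit from a mixed model for repeated measures fitted within each cohort. Include visit and baseline score, with an unstructured covariance and a named simpler fallback. Use all subjects with a baseline and at least one post-baseline score.
3. As a sensitivity analysis, repeat the model with scores collected after progression while the subject is still on study treatment, cutting off at the start of post-study treatment.

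The cost is SAP wording and one standard model per scale, plus its repeat; no new data are needed. The model assumes missing at random, so it reduces the bias but may not remove it. It also implicitly extrapolates scores beyond death. In cohorts of about 30 the estimates will be imprecise and the simpler covariance may be needed. If the model is not adopted, step 1 alone would still tell the reader whom the means describe.
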